#### **12.4 Long-term Follow-up, post 52-weeks visit (Every 6 Months: Months 18-30 ( $\pm 4$ wks) and 3 yrs ( $-3$ wks/ $+4$ wks))**

At 52 weeks, subjects will be allowed to continue with the study device with a follow-up office visit every 6 months for a maximum of three years post study device placement. During these visits, the following will be performed:

- Vital signs and weight
- Pelvic exam (string check)
- Transvaginal ultrasound If unable to confirm IUD placement by string check or if indicated
- Pregnancy test, urine
- Interval and concurrent medications
- Adverse events
- Concomitant contraception
- Need for contraception (If a subject believes the study device may have been expelled or is no longer in place, the subject should call for an urgent study visit and refrain from having sex or use appropriate non-hormonal contraception until further evaluation is completed. (See Section 4.7 for details)
- Verify sexual activity and any back-up method is documented
- Instruct the subject to contact the site immediately if she thinks she has become pregnant.

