### **LevoCept Safety-Related Removal Rates and Expulsion Rates**

Cumulative LevoCept safety-related removal rates and expulsion rates at each year will be summarized.

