4. Bleeding and spotting

The total number of bleeding or spotting days for each subject at each cycle will be counted. The total number of bleeding and spotting days for each subject at each cycle will also be counted separately.

5. Discontinuation rate and reasons for discontinuation

Removal rates

The removal rate is defined as the percentage of the number of subjects with device removed among the total number of subjects enrolled in the study by that time-point.

Expulsion rates

The expulsion rate is defined as the percentage of the number of subjects with device expulsion among the total number of subjects enrolled in the study by that time-point.

Discontinuation rate

The discontinuation rate is defined as the percentage of the number of subjects discontinued study among the total number of subjects enrolled in the study by that time-point.

Reasons for discontinuation

The following reasons have been collected for exiting study:

- Adverse Event;
- Withdrew Consent;
- Protocol Violation;
- Lost to Follow-up;
- Investigator/Sponsor Decision;
- Pregnancy;
- Screen Failure;
- Other.

5 Analysis Populations

Data analyses will be based on the analysis populations defined below. Analysis populations, including exclusions based on major protocol deviations (PDs), will be reviewed and approved by the Sebelia and its designee. Excluded cases will be documented together with the reason for exclusion.

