6.2.9.7 Device Expulsion and Removal

Device expulsion will be recorded daily by the subject in e-diary. Device removal procedure will be recorded in the CRF. Cumulative study device removal rates and expulsion rates will be summarized at 1-year (study day 1 - 364), 2-year (study day 365 - 728), and 3-year (study day 729 +).

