Some Pain	n (%)
Painful	n (%)
Moderately Painful	n (%)
Very Painful	n (%)
Medication given during the procedure	
n	n
Yes	n (%)
No	n (%)
Mechanical Dilatation	
n	n
Yes	n (%)
No	n (%)

Note: Percentages are based on the number of subjects specified in the column header, i.e. N, unless small n is specified for each category.

Reference: Listing xxx.

Program Location: \\xx\xxx\xxx\xxx\xxxxxx\xxxxxxxxxxxxxxxx\xxxx\xxxxx.sas

date

time

CONFIDENTIAL

Sebela Pharmaceuticals Development LLC
CMDOC-0022

Page x of y

Table 14.3.5.3
Device Expulsion/Removal and Subject Pain During the Procedure (Safety Population)

Description	All Subjects (N=xx) n (%)
Cumulative 1-Year Device Expulsion Rate	n (%)
Cumulative 1-Year Device Removal Rate	n (%)
Cumulative 2-Year Device Expulsion Rate	n (%)
Cumulative 2-Year Device Removal Rate	n (%)
Cumulative 3-Year Device Expulsion Rate	n (%)
Cumulative 3-Year Device Removal Rate	n (%)
Device Expel Prior to This Visit	
n	n
Yes	n (%)
No	n (%)
If Yes, Expulsion Status	
n	n
Complete	n (%)
Partial	n (%)
Was removal accomplished by pulling the strings Without Difficulty	
n	n
Yes	n (%)
No	n (%)
If No, Select All That Apply:	
n	n (%)
Required significant force to pull out with strings	n (%)
Required use of ultrasound guidance	n (%)
Required use of Alligator forceps	n (%)
Required use of IUD hook	n (%)
Required use of other instrument	n (%)
Unable to remove in office initially, required second office visit for successful removal	n (%)
Unable to remove in office - removed in OR	n (%)
Other	n (%)

Note: Percentages are based on the number of subjects specified in the column header, i.e. N, unless small n is specified for each category.
Reference: Listing xxx.

Program Location: \\xx\xxx\xxx\xxxxxx\xxxxxxxxxxxxxxxx\xxxx\xxxxx.sas

date

time

CONFIDENTIAL

Sebela Pharmaceuticals Development LLC
CMDOC-0022

Page x of y

Table 14.3.5.3
Device Expulsion/Removal and Subject Pain During the Procedure (Safety Population)

Programmers note: Continued table

Description	All Subjects (N=xx) n (%)
Ease of Device Removal	
n	n
Very Easy	n (%)
Easy	n (%)
Neither Easy nor Difficult	n (%)
Difficult	n (%)
Very Difficult	n (%)
Device Removal Pain	
n	n
No Pain	n (%)
Some Pain	n (%)
Painful	n (%)
Moderately Painful	n (%)
Very Painful	n (%)
Medication Given During the Procedure	
n	n
Yes	n (%)
No	n (%)

Note: Percentages are based on the number of subjects specified in the column header, i.e. N, unless small n is specified for each category.

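### The SAP reports all-cause device removal where the protocol plans safety-related removal by year, so planned removals count as events and the change is not declared

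*SAP*

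**What the plan says.** Protocol 20.7, under its heading on safety-related removal and expulsion, states: "Cumulative LevoCept safety-related removal rates and expulsion rates at each year will be summarized". It does not define safety-related.

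SAP 4.2, item 5, gives a different quantity: "The removal rate is defined as the percentage of the number of subjects with device removed among the total number of subjects enrolled". No reason for removal is required, and nothing is said about excluding or censoring planned removals.

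SAP 6.2.9.7 carries this into the analysis: "Cumulative study device removal rates and expulsion rates will be summarized at 1-year (study day 1 - 364". The second window is days 365 to 728. The third is given as "and 3-year (study day 729" followed by a plus sign, so it has no upper end. The shell of Table 14.3.5.3 has matching rows, the last being "Cumulative 3-Year Device Removal Rate", with no breakdown by reason.

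Protocol 12.3.1 and 12.4.2 make device removal part of the exit visit, before and after Week 52 respectively. Protocol 12.4 allows continued use with a "follow-up office visit every 6 months for a maximum of three years post study device placement". SAP 8.2 lists two changes to the planned analyses, both about populations. The removal rate is not among them.

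**The concern.** A safety-related removal rate tells the reader how often the device had to come out because of harm. An all-cause rate in this trial mixes that with removals that happen by design: women who finish at Week 52, women who reach the three-year limit, and women who stop in order to conceive. A partly expelled device that is then taken out can also appear in both the removal and the expulsion row.

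The trial is meant to provide safety and effectiveness data to support a Phase III study. If the only by-year removal result is set largely by the visit schedule, it does not answer the question Protocol 20.7 put. A reader of the clinical study report would not learn from SAP 8.2 that the quantity had changed. The same tables are run at the one-year interim (SAP section 7), so both reports are affected.

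**Working it through.** The documents state no removal figure, so there is none to reproduce. The check applies the SAP definition and asks what the result depends on.

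**Year 3**

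From the documents: planned enrolment of 250; enrolled means that placement was attempted, successfully or not (SAP 5.2); use capped at three years; removal at exit. Women lost to follow-up may keep the device (Protocol 12.8).

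Assumed, because the documents give no values: f = share of enrolled with failed placement; e = share of placed women who expel; l = share of placed women lost with the device in place; s = share of placed women with a safety-related removal. Expelled devices are counted here as expulsions only.

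At the end of follow-up every placed device has been expelled, left in a woman who was lost, or removed. Hence:

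- SAP 3-year rate, per enrolled = (1 − f)(1 − e − l)
- Safety-related rate, per enrolled = (1 − f) × s

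| f | e | l | SAP 3-year rate (enrolled) | Same, Safety Population |
|---|---|---|---|---|
| 0 | 0 | 0 | 100% | 100% |
| 2% | 3% | 5% | 0.98 × 0.92 = 90.2% | 92% |
| 2% | 4% | 10% | 0.98 × 0.86 = 84.3% | 86% |
| 5% | 5% | 20% | 0.95 × 0.75 = 71.2% | 75% |
| 3% | 5% | 30% | 0.97 × 0.65 = 63.0% | 65% |

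The quantity s does not appear in the first formula. In the third row the SAP rate is 84.3% whether s is 2%, 10% or 25%. The safety-related rate would be 0.98 × s = 2.0%, 9.8% or 24.5%. This holds f, e and l fixed as s varies.

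**Year 1**

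SAP 6.2.9.7 closes the first year at day 364, while SAP Table 1 puts Week 52 at day 365. Planned Week 52 removals therefore fall into Year 1 or Year 2 according to the visit date.

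Assumed: 250 placed; 65% to 80% complete Year 1; 30% to 50% of completers leave at Week 52; visits uniform over the window.

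- Planned removals = 250 × completion × share leaving: 250 × 0.80 × 0.30 = 60; 250 × 0.70 × 0.40 = 70; 250 × 0.65 × 0.50 = 81.
- Days 351 to 364 are 14 days. Week 52 ± 2 weeks is days 351 to 379, or 29 days. SAP Table 1 prints days 351 to 385, or 35 days.

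| Planned removals | On or before day 364, at 14/29 | Points on 250 | On or before day 364, at 14/35 | Points on 250 |
|---|---|---|---|---|
| 60 | 29 | 11.6 | 24 | 9.6 |
| 70 | 34 | 13.5 | 28 | 11.2 |
| 81 | 39 | 15.7 | 33 | 13.0 |

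The range over both windows is about 10 to 16 percentage points. The rest of the planned Week 52 removals enter in Year 2.

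**What else the SAP tabulates**

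| Output | What it gives | Cumulative safety-related removal by year? |
|---|---|---|
| Table 14.3.1.1.1, row on AEs leading to removal | Overall events and n (%) | No, one total |
| Table 14.3.1.5 | Same, by system organ class and preferred term | No, one total |
| Table 14.1.1 | AE exits, 1-year study and extension | No, counts study exits and pools Years 2 and 3 |
| Table 14.3.5.3 | Removal at 1, 2 and 3 years | By year, but all-cause |

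**Denominator**

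SAP 4.2 divides by enrolled subjects. Table 14.3.5.3 is headed Safety Population and bases percentages on the column N, which SAP 5.3 limits to successful placements. The gap in the first table is 0 to about 4 points (75% against 71.2%).

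**The case against.** The strongest reply is that safety-related removal has not disappeared from the SAP. AEs leading to removal are tabulated overall and by preferred term. AE exits are shown separately for the 1-year study and the extension, and since removal belongs to the exit visit and devices are not replaced, these should follow AE-driven removal closely. The interim run of Table 14.3.1.5 gives an approximate Year 1 count, and listings hold days on device and exit reason for each woman. The protocol's listed tolerability outcome, discontinuation and its reasons, is still delivered. The missing rate is one undefined descriptive line in a single-arm study with no formal sample size calculation.

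Most of this stands, and it limits the seriousness of the point. A reader might infer that the SAP leaves the safety question about removal unanswerable; the tables above show otherwise. They still do not give the by-year cumulative rate. The interim count is also not a clean Year 1 figure: with about five months of enrolment, the earliest women may have about 12 + 5 = 17 months of follow-up when the last woman completes a year.

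A reader might also infer that the 3-year figure must approach 100% whatever the device's safety. The documents do not support that. 100% is a ceiling, reached only with no failed placements, expulsions or losses, and the documents give none of these. What follows from the SAP definition is narrower: the figure is fixed by those losses and not by safety-related removals.

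Finally, the Year 1 size rests on completion and continuation rates that appear nowhere in the documents. Only the direction is secure, provided some completers have the device out before day 365.

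**Conclusion.** The point holds as a departure from Protocol 20.7. The SAP defines and reports all-cause removal where the protocol plans safety-related removal at each year, and SAP 8.2 does not say so. Table 14.3.5.3 would show a 3-year rate somewhere between about 63% and 100% under the assumed losses, unrelated to s when those losses are fixed. Its 1-year rate would carry about 10 to 16 points of planned removals under the assumed completion, leaving and visit timing.

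The gap is specific: no cumulative safety-related removal rate by year. Crude AE-related removal counts remain. The issue is descriptive and does not affect the Pearl Index. It should be fixed.

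**What to change.** In SAP 4.2 item 5, SAP 6.2.9.7 and Table 14.3.5.3:

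1. Define safety-related removal from data already collected, for example a removal linked to an AE whose recorded action with the study device is removal (Listing 16.2.7.1). The protocol gives no definition, so the SAP must choose one and state it.
2. Report its cumulative incidence from placement at Years 1, 2 and 3. Censor planned end-of-study removals. Censor other non-safety removals and expulsions, or treat them as competing events, and state which. A crude proportion is not enough: women who leave as planned at Week 52 would stay in the denominator and dilute the later years.
3. State once whether removal of a partly expelled device counts as an expulsion or a removal, so that it is not counted twice. Either can be defended, since Protocol 20.7 lists partial expulsion among the events for special attention.
4. If all-cause removal is kept, show it separately by reason, as disposition.
5. Use one denominator, enrolled or Safety Population, in both the text and the table.
6. List any remaining departure from Protocol 20.7 in SAP 8.2.

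The cost is SAP wording and one table shell. Removal and expulsion dates (Listing 16.2.5.2), AE action taken and exit reasons are already collected.

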5.1 All Screened

Screened subjects are all subjects who have signed informed consent, PHI and Bill of Rights forms (if applicable) and being found eligible based on their history, physical examination, screening tests. Patients who withdraw consent before insertion for any reason would be considered a screen failure.

5.2 All Enrolled

Enrolled subjects are all screened subjects who underwent the study device placement procedure, regardless of whether the study device was successfully placed or not.

5.3 Safety Population

The safety analysis population will include all enrolled subjects who underwent a successful study device placement procedure.

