### **Safety and Other Outcome Measures**

LevoCept ease of placement, placement success, expulsions, and removal success will be descriptively summarized.

Safety evaluations will be based on the incidence of adverse events and serious adverse events and by relationship to the study device or study device placement procedure.

Study device tolerability will be based on changes in bleeding and spotting patterns and study discontinuation (including reasons for discontinuation).

Safety analyses will be based on the experience of all subjects who had attempted study device placement and provided any relevant data. Tolerability analyses will be based on the experience of all subjects who received a study device and provided any relevant data.

Subjects will record frequency and intensity of vaginal bleeding through a daily e-diary. The number of bleeding or spotting days will be summarized for each cycle. In addition, bleeding and spotting will each be summarized separately. Bleeding analyses will include all subjects who had a study device placed and have at least 1 cycle where they were not pregnant and were providing bleeding-related e-diary data on the days in the reference period.

In general, summaries of quantitative variables will include the sample size, mean, median, standard deviation, minimum, and maximum. For qualitative (categorical) variables the summaries will include the number and percentage of subjects in each category.

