## **12.2 Visit 2: LevoCept Placement (Day 1)**

See Section 4.1 for LevoCept insertion timing instructions. Subjects must have a negative urine pregnancy test just prior to LevoCept placement. Initiation of the LevoCept is consistent with standard IUD placement. Refer to the Clinician's Quick Use Guide and Investigator's Brochure for specific instructions.

If placement is unsuccessful, a second attempt may be made on the same day or within one (1) week following the first attempt. If a second attempt is also unsuccessful, the subject will be discontinued early from the study. The need for cervical dilation to facilitate placement of LevoCept will be left to the discretion of the investigator and subject; however, it is recommended that placement be tried first without prior cervical dilation. Use of cervical dilation will be recorded on the case report form. The need for pain control will also be left to the discretion of the investigator and subject. Any medications given for pain control will be recorded on the Concomitant Medications case report form.

Prior to LevoCept placement, the following evaluations will be completed:

- Entry criteria confirmed
- Vital signs and weight
- Pelvic Exam
- Pregnancy test, urine
- Prior and concurrent medications
- Any adverse events.

Following LevoCept placement, the following will be performed:

- LevoCept placement ease
- LevoCept placement pain
- LevoCept position (evaluated by Transvaginal Ultrasound)
- Concomitant contraception
- Need for contraception if LevoCept was not properly placed (If a subject believes the study device may have been expelled or is no longer in place, the subject should call for an urgent study visit and refrain from having sex or use appropriate non-hormonal contraception until further evaluation is completed. (See Section 4.7 for details)

- Review the completed practice diaries and discuss with the subject any further training that is required and answer any questions the subject may have about how to correctly complete the diaries.
- Instruct the subject to contact the site immediately if she thinks she has become pregnant.

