### 15.2 Definition of An Adverse Event

An **adverse event** is any untoward medical occurrence in a clinical investigation subject administered an investigational product and which does not necessarily have to have a causal relationship with this treatment. An AE can, therefore, be any unfavorable and unintended sign (that could include a clinically significant abnormal laboratory finding), symptom, or disease temporally associated with the use of a medicinal product, whether or not considered related to the medicinal product.

- Any medical condition or clinically significant laboratory abnormality with an onset date before the first date of attempted study device placement is usually considered to be pre-existing, and should not be documented in the eCRF as an AE, unless there is an increase in frequency or intensity of that AE, but should be recorded as medical history.
- Any AE (i.e., a new event or an exacerbation of a pre-existing condition) with an onset from the first attempt of study device placement through Study Exit should be recorded as an AE on the eCRF. All AEs must be recorded on the AE eCRF regardless of the severity or relationship to study device. It is important that Investigators also report all AEs that result in expulsion or removal of the investigational product being studied, whether serious or non-serious.

Pregnancy is an outcome, and not an adverse event in this study.

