### **20.1 Analysis Populations**

The following analysis populations will be created:

All Enrolled: All subjects enrolled into the study.

Intent to Treat (ITT) / Safety: All enrolled subjects who underwent the study device placement procedure, regardless of whether the study device was successfully placed or not.

Evaluable for Pregnancy (EP):

Subjects must meet requirements 1 and 2 to be EP. Subjects must also meet either requirement 3 or requirement 4 to be EP.

1. between 18 to 35 years of age (inclusive) at enrollment
2. at least one report of pregnancy status after being enrolled  
AND
3. have at least 1 cycle of e-diary with intercourse and without any  
backup contraception or emergency contraception (EC)  
OR
4. became pregnant while LevoCept was in place.

Evaluable for Cycle Control (ECYC): all subjects Evaluable for Pregnancy with at least one cycle for which: A) a pregnancy did not occur; and B) there is bleeding related e-diary data.

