1.2 Definitions

The following visits are scheduled in the study protocol:

- Visit 1(Screening Visit);
- Visit 2 (LevoCept Placement Visit): Day1;
- Follow up Visit 3 - 6 : Week 6 \pm 1w,13 \pm 2w, 26 \pm 2w and 52 \pm 2w;
- Long term follow up (LTFU): Every 6 months post 52 weeks (max 3 years post insertion) \pm 2w.

Day 1 is defined as the date of study device successful deployed.

Based on the visit window in the study protocol, new analysis visit windows are redefined as follows to cover every data point, including unscheduled visits. Also note that if there are 2 or more non-missing records in the same analysis visit window, only the last one (by the assessment date) will be used for summary table, but data listings will include all records for all enrolled subjects, unless stated otherwise. For clinical data, visits will be referred to by their study day throughout this document.

The visit windows and study days are presented in Table 1:

Table 1 Visit windows and study days

Visit	Visit (Window) in Protocol	Study Day	Visit (Window) in Protocol in study day	Analysis Visit Window in study day
Visit 1(Screening)	Visit 1/Screening		-1 or earlier	-1 or earlier
Visit 2(Placement)	Visit 2 (Day 1)	1	1	1
Visit 3	Visit 3 (Week 6 \pm 1w)	43	36-56	2 – 68
Visit 4	Visit 4 (Week 13 \pm 2w)	92	78-112	69 – 138
Visit 5	Visit 5 (Week 26 \pm 2w)	183	169-203	139 – 274
Visit 6	Visit 6 (Week 52 \pm 2w)	365	351-385	275 – 385
Visit 7 Long Term FU 1	Visit 7 LTFU 1/Year 2 Month 6 (Week 78 \pm 2w)	547	533-567	386 – 638
Visit 8 Long Term FU 2	Visit 8 LTFU 2/Year 2 Month 12 (Week 104 \pm 2w)	729	715-749	639 – 821
Visit 9 Long Term FU 3	Visit 9 LTFU 3/Year 3 Month 6 (Week 130 \pm 2w)	912	897-930	822 – 1003
Visit 10 Long Term FU 4	Visit 10 LTFU 4/Year 3 Month 12 (Week 156 \pm 2w)	1093	1079-1113	1004 +

The analysis cycles and study days are presented in Table 2:

Table 2 Analysis cycles and study days

Year	Analysis Cycle	Study Day	Year	Analysis Cycle	Study Day	Year	Analysis Cycle	Study Day
Year 1	Cycle 1	1-28	Year 2	Cycle 14	365-392	Year 3	Cycle 27	729-756
Year 1	Cycle 2	29-56	Year 2	Cycle 15	393-420	Year 3	Cycle 28	757-784
Year 1	Cycle 3	57-84	Year 2	Cycle 16	421-448	Year 3	Cycle 29	785-812
Year 1	Cycle 4	85-112	Year 2	Cycle 17	449-476	Year 3	Cycle 30	813-840
Year 1	Cycle 5	113-140	Year 2	Cycle 18	477-504	Year 3	Cycle 31	841-868
Year 1	Cycle 6	141-168	Year 2	Cycle 19	505-532	Year 3	Cycle 32	869-896
Year 1	Cycle 7	169-196	Year 2	Cycle 20	533-560	Year 3	Cycle 33	897-924

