6.2.9.1 Adverse Events

Number of AEs will be summarised by SOC and/or PT for the following categories of TEAEs: all AEs, SAEs, AEs related to study device, AEs related to study device placement/removal procedure, AEs leading to death, AEs leading to study device removal and AEs as primary reason for exiting study. Patients with more than one occurrence of the same SOC (PT) will be counted only once within the SOC (PT) categorisation.

AEs will also be summarised similarly by severity (i.e. mild, moderate, severe), relationship to study device (i.e. not related, unlikely related, probably related, related), relationship to placement/removal procedure (i.e. not related, unlikely related, probably related, related) and onset time frame (i.e. 0-3 months, >3-6 months, >6-12 months, >12 months). Should a subject experience more than one occurrence of the same SOC (PT), the subject's worst occurrence (worst intensity/most related causality) will be retained in the tabulation.

All AEs, including AEs that started prior to the study device placement, will be presented in data listings. In addition, separate listings of all SAEs, AEs related to study device, AEs related to study device placement/removal procedure, AEs leading to death, AEs leading to study device removal and AEs as primary reason for exiting study will be provided. In case of any AEs reported from study device insertion failure subjects, selected AE tables will be repeated for all enrolled subjects for all AEs.

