10.3 Standard Calculations

Variables requiring calculation will be derived using the following formula.

- **Study Day** – Study Day 1 is defined as the date of the study device placement; the day before the study device placement is defined as Study Day -1. For a given event date, Study Day is calculated relative to the date of study device placement.

Study Day = [Event Date – Study Device Placement Date] (in days) + 1 day,
where the event date is on or after the study device placement date.

Study Day = [Event Date – Study Device Placement Date] (in days),
where the event date is before the study device placement date.

- **Age (Years)** – Age is calculated as the number of years from the date of birth to the date of informed consent using the following formula and rounded down to the nearest year.

$$\text{Age (years)} = \frac{\text{Date of informed consent} - \text{date of birth}}{365.25}$$

- **Height** – Height entries made in inches (in) are converted to centimeters using the following formula:

Height (cm) = Height (in) * 2.54, rounded to the one decimal place.

- **Weight** – Weight entries made in pounds (lbs) are converted to kilograms (kgs) using the following formula:

Weight (kg) = Weight (lb) / 2.2046, rounded to the one decimal place.

- **Body Mass Index (BMI)** – BMI is derived using following formula and rounded to one decimal place.

$$\text{BMI (kg/m}^2\text{)} = \frac{\text{weight(kg)}}{[\text{height(cm)}/100]^2}$$

BMI categorized by Underweight (< 18.5), Normal (18.5 – 24.9), Overweight (25.0 – 29.9), and Obese (\geq 30.0).

CONFIDENTIAL

11 Appendix 1: Partial Date Conventions

Imputed dates will NOT be presented in the listings.

Algorithm for Treatment Emergence of Adverse Events:

Start Date	Stop Date	Action
Known	Known/Partial/Missing	If start date < study med start date, then not TEAE; If start date ≥ study med start date, then TEAE.
Partial, but known components show that it cannot be on or after study med start date	Known/Partial/Missing	Not TEAE
Partial, could be on or after study med start date	Known	If stop date < study med start date, then not TEAE; If stop date ≥ study med start date, then TEAE.
	Partial	Impute stop date as latest possible date (i.e. last day of month if day is unknown or 31 December if day and month are unknown), then: If stop date < study med start date, then not TEAE; If stop date ≥ study med start date, then TEAE.
	Missing	Assumed TEAE

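### The SAP narrows the safety population to successful placements without a reason and leaves the TEAE start undefined, so the Safety-population tables can understate insertion harm

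*SAP*

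**What the plan says.** **Protocol.** Section 20.1 defines the ITT/Safety population as "All enrolled subjects who underwent the study device placement procedure, regardless of whether the study device was successfully placed or not". The synopsis agrees: "Safety analyses will be based on the experience of all subjects who had attempted study device placement and provided any relevant data". Section 20.7 applies that population to all safety measures unless noted otherwise. It asks for AE summaries by relationship to the placement or removal procedure and by severity. Under section 15.2, any AE "with an onset from the first attempt of study device placement through Study Exit should be recorded as an AE". Under section 12.2, after an unsuccessful placement "a second attempt may be made on the same day or within one (1) week following the first attempt".

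**SAP, population.** Section 5.3 states: "The safety analysis population will include all enrolled subjects who underwent a successful study device placement procedure". Section 6.2.9 makes this the default for safety analyses. Section 8.2 lists the change from the protocol but does not explain it. The wider protocol set survives under another name, as All Enrolled (section 5.2).

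**SAP, timing.** Section 1.2 states: "Day 1 is defined as the date of study device successful deployed". Appendix 1 says, for a known onset date: "If start date < study med start date, then not TEAE".

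**SAP, safeguard.** Section 6.2.9.1 provides that, if insertion-failure subjects report AEs, "selected AE tables will be repeated for all enrolled subjects for all AEs".

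**The concern.** Device placement and safety are both stated objectives. Protocol 15.3.1 has any untoward event during the placement procedure recorded as related to that procedure. Whether placement succeeds is known only after the procedure has been carried out. A safety population restricted to successes therefore conditions on an outcome of the exposure being assessed. If difficult or failed insertions cause more procedural harm than easy ones, which is plausible but cannot be shown from the documents, the restriction lowers the reported procedure-related AE rates. The effect falls on the tables where a reader would look for insertion harm. A late or unclear start for treatment emergence could remove further first-attempt events, this time from women who are in the Safety population.

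**Working it through.** The plan states no figure on this point that could be reproduced. The check compares definitions, traces where events would appear, and then gives an illustration under assumed failure rates.

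**1. Population.** Protocol 20.1 and the synopsis count every attempted placement; SAP 5.3 counts successful placements. The difference is exactly the women with no successful placement.

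**2. TEAE anchor.** The SAP uses three:
- Section 4.2: during or after *exposure to the study device*, with no date.
- Appendix 1: *study med start date*, a term the SAP does not define.
- Table footnotes (for example Table 14.3.1.3.1): the date/time of *study device placement*, without saying first attempt or successful placement.

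Section 1.2 puts Day 1 at successful deployment, section 10.3 puts Study Day 1 at device placement, and Listing 16.2.7.1 counts study days from successful deployment. Together they suggest that placement means successful deployment. This is an inference; no sentence in the SAP states it.

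**3. Example of the timing effect.** Let the first attempt fail on date d with an AE that day, and let the second succeed on d + 7, the longest gap allowed. By the SAP 10.3 formula for events before placement, Study Day = d − (d + 7) = −7. On the reading in step 2, Appendix 1 classes the AE as not treatment-emergent, although protocol 15.2 records it.

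**4. Tracing an AE of a failed attempt.**

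| Woman | In SAP Safety population? | Safety-population TEAE tables |
|---|---|---|
| No successful placement | No | Absent from all |
| Success on a later day | Yes | Absent on the successful-deployment reading |
| Success on the same day | Yes | Kept by the date rule in Appendix 1; the date/time footnote could drop it |

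In all three cases the AE belongs in the All Enrolled outputs: Tables 14.3.1.1.2 (overall), 14.3.1.2.2 (severity and relatedness), 14.3.1.3.2 (SOC and PT) and 14.3.1.4.2 (SAEs), Tables 14.3.2.1 to 14.3.2.3 where applicable, and Listings 16.2.7.1 to 16.2.7.5.

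**5. What the All Enrolled outputs lack.** Tables 14.3.1.5 to 14.3.1.13 have no All Enrolled version. Table 14.3.1.2.2 gives relatedness and severity without event terms; Table 14.3.1.3.2 gives terms without relatedness or severity. No table shows which procedure-related events (14.3.1.10), or which severe events (14.3.1.8), occurred across all attempts. Also, the trigger in section 6.2.9.1 names only insertion-failure subjects, so a woman placed at the second attempt does not activate it.

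**6. Illustration.** Planned enrolment is up to 250 (protocol synopsis). The failure rate f is an **assumption**, taken from 1% to 8%. Failures = 250 × f; Safety N = 250 − failures. Suppose one woman with a failed placement has a given insertion event and nobody else does. Upper limits are from exact two-sided 95% intervals. For 0/n the limit is 1 − 0.025^(1/n). For 1/250 it is the 97.5th percentile of Beta(2, 249), which is 2.21%.

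| Assumed f | Failures | SAP Safety result | Upper limit | Protocol population |
|---|---|---|---|---|
| 1% | 2 (2.5 rounded down) | 0/248 | 1.48% | 1/250 = 0.4%, upper 2.21% |
| 2% | 5 | 0/245 | 1.49% | same |
| 4% | 10 | 0/240 | 1.53% | same |
| 8% | 20 | 0/230 | 1.59% | same |

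The outer bound, in which every failed placement has the event, is 2/250 = 0.8% to 20/250 = 8.0% in the protocol population, against 0% in the SAP Safety population.

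**The case against.** The strongest reply is that the SAP already handles most of this. All Enrolled in SAP 5.2 is the protocol's safety set. The index lists the four All Enrolled AE tables without any condition. They are titled for adverse events rather than treatment-emergent events, and section 6.2.9.1 says all AEs, so first-attempt events appear whatever the TEAE anchor. Following their templates, Table 14.3.1.1.2 has a row for procedure-related AEs and Table 14.3.1.2.2 crosses severity with procedure relatedness. Listing 16.2.7.3 shows every procedure-related AE in enrolled women. The change is disclosed, the study is a single-arm Phase II trial with descriptive safety, and the primary endpoint is not touched.

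Most of this stands, and it rules out three stronger conclusions that a reader might draw:
- *That these events disappear from reporting.* They do not. The single event in the illustration would still be counted as 1/250 in Table 14.3.1.3.2.
- *That the SAP starts TEAEs at successful deployment.* That is the natural reading of sections 1.2 and 10.3 with Appendix 1, but the documented defect is an inconsistent and partly undefined anchor.
- *That a known number of women have AEs outside the TEAE tables.* Assuming 2% to 4% final failures and another 2% to 4% later-day successes gives 250 × 4% to 250 × 8% = 10 to 20 women. That counts women under assumed rates, not AEs.

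The reply does not supply a reason for departing from the protocol, an All Enrolled breakdown by event term of procedure relatedness or severity, or a section 6.2.9.1 trigger that matches the index.

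**Conclusion.** The point holds in limited form. The SAP replaces the protocol's safety population with a narrower one and gives no reason. The main TEAE tables therefore omit women whose placement failed. The TEAE start is ambiguous and, on its natural reading, also excludes first-attempt events in women placed on a later day. The All Enrolled outputs keep the events visible but do not show procedure relatedness or severity by event term.

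The numerical effect is probably small: in the illustration, 0% instead of 0.4% for a single event, with an upper limit of about 1.5% to 1.6% instead of 2.2%. Those figures rest on an assumed failure rate of 1% to 8% and on one assumed event. The bias is towards understatement if failed attempts carry more procedural AEs than successful ones. This should be corrected before analysis, but it does not threaten the trial's main conclusion.

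**What to change.** - **Population (SAP 5.3, 8.2).** Define Safety as all subjects with any placement attempt, as in protocol 20.1.
- **TEAE onset (SAP 4.2, Appendix 1, table footnotes).** Define *study med start date* and TEAE onset as the date of the first placement attempt, and use that one definition throughout.
- **Tables.** Run the general AE tables, including 14.3.1.8 and 14.3.1.10, on the restored population. The conditional wording in section 6.2.9.1 is then no longer needed.
- **On-device outcomes.** Keep a separate, named successful-placement set for bleeding, expulsion, removal, AEs leading to device removal (14.3.1.5) and the later onset time frames in 14.3.1.12 and 14.3.1.13. A woman without a device cannot have a removal event, and counting her in late-onset denominators would dilute on-device rates. For this reason the AE tables should not all be moved to the all-attempts set.
- **Dependent definitions.** SAP 5.6 (ECYC) refers to safety subjects and should point to the successful-placement set. SAP 5.5 (EP) already requires successful placement, so the Pearl Index is unchanged.

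The cost is SAP wording, slightly different denominators and one more analysis set. No new data are needed, because Listing 16.2.5.1 already carries the date of each attempt.
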